SUD period: defined as the period between a patient's first 44mg/1.1mL vial of elranatamab and first 76mg/1.9mL vial of elranatamab, inclusive. See Section 9.3.1 and Annex 1 for more details. Within the SUD period, three sub-periods are identified:

- **Overall:** defined as the period between first 44mg/1.1mL vial and first 76mg/1.9mL vial of elranatamab.
- **First 44mg/1.1mL vial – Second 44mg/1.1mL vial:** defined as the period between the two 44mg/1.1mL vials of elranatamab, if second 44mg/1.1mL vial is administered.
- **Second 44mg/1.1mL vial – first 76mg/1.9mL vial:** defined as the period between the second 44mg/1.1mL vial and the first 76mg/1.9mL vial of elranatamab, if second 44mg/1.1mL vial is administered.

Follow-up period: defined as the period between the first hospital claim for elranatamab (index date) and the end of the hospital claim of the last elranatamab administration. Within this follow-up period, five sub-periods are identified (when sufficient follow-up time is available at the patient level). These sub-periods allow for reporting study endpoints across different phases of the follow-up period, and are based on expected dosing administrations and schedule of patients with switch to bi-weekly administrations from label guidance (see [Table 10. Dosing Schedule of Elranatamab during Follow-up Period for Patients Switching to](#)

[Q2W](#) and [Table 11. Dosing Schedule of Elranatamab during Follow-up Period for Patients staying on QW](#)):

- **Index date to day 8:** defined as the first 8 days post-index date, inclusive. Also defined as day 1 to day 8.
- **Day 9 to day 168:** defined as the period from day 9 to day 168 post-index date.
- **Day 169+:** defined as the period from day 169 post-index date to end of follow-up period.

- **Overall follow-up:** defined as the period from index date to end of follow-up period.

IVIG follow-up assessment period: defined as the 30-day window post index date. If a patient has fewer than 30 days of data available post to the index date, the assessment window will be equal to the maximum number of days available post to the index date.

CRS/ICANS follow-up assessment period: defined as the 14-day window post index date. If a patient has fewer than 14 days of data available post to the index date, the assessment window will be equal to the maximum number of days available post to the index date.

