Abbreviations: CAR-T: chimeric antigen receptor T-cell therapy; IMiDs: immunomodulatory agents; IVIG: intravenous immunoglobulin; PI: proteasome inhibitors; SCT: stem cell transplant;

Table 7. Variables for Outcomes (Objective 5 – Known Adverse Events)

Variable	Role	Data Source	Operational Definition	
			Definition	Assessment Period(s)
CRS events ¹	Outcome	MDV	Disease code for CRS (Yes/No)	CRS/ICANS follow-up

Variable	Role	Data Source	Operational Definition	
			Definition	Assessment Period(s)
			(14) Incidence and prevalence will be reported, see Section 9.7.2 for additional details.	assessment period
Frequency of CRS events	Outcome	MDV	Total number of CRS events during the time period per patient (categorical) 
 • 1 CRS event • 2 CRS events • 3 or more CRS events 	CRS/ICANS follow-up assessment period
CRS Concomitant medications	Outcome	MDV	Disease code for concomitant medications (i.e., IV hydration) received on the same day as the CRS event (Yes/No)	CRS/ICANS follow-up assessment period
Length of stay for CRS events	Outcome	MDV	The total time in days of the CRS hospital stays among patients who have at least 1 CRS event (continuous).	CRS/ICANS follow-up assessment period
Days from index to first CRS event	Outcome	MDV	Time in days from index date to first CRS event (continuous)	CRS/ICANS follow-up assessment period
ICANS events ¹	Outcome	MDV	Disease code for ICANS (Yes/No) Incidence and prevalence will be reported, see Section 9.7.2 for additional details.	CRS/ICANS follow-up assessment period
Frequency of ICANS events	Outcome	MDV	Total number of ICANS events during the time period per patient (categorical) 
 • 1 ICANS event • 2 ICANS events 	CRS/ICANS follow-up assessment period

090177e1a4a71ff1\Approved\Approved On: 05-Nov-2025 14:15 (GMT)

Variable	Role	Data Source	Operational Definition	
			Definition	Assessment Period(s)
			
 3 or more ICANS events 	
ICANS Concomitant medications	Outcome	MDV	Disease code for concomitant medications (i.e., IV hydration) received on the same day as the ICANS event (Yes/No)	CRS/ICANS follow-up assessment period
Length of stay for ICANS events	Outcome	MDV	The total time in days of the ICANS hospital stays among patients who have at least an IP stay with ≥ 1 ICANS event (continuous).	CRS/ICANS follow-up assessment period

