Days from index to first ICANS event	Outcome	MDV	Time in days from index date to first ICANS event (continuous)	CRS/ICANS follow-up assessment period
Cytopenia occurrence ¹	Outcome	MDV	Disease code or labs value for cytopenias occurrences (Yes/No): 
 Anemia Leukopenia Lymphopenia Neutropenia Thrombocytopenia Number and proportion of patients with a health claim code for each cytopenia will also be reported. Incidence and prevalence will be reported, see Section 9.7.2 for additional details.	SUD period
Days from index to first cytopenia	Outcome	MDV	Time in days from index date to first cytopenia (continuous)	SUD period

090177e1a4a71ff1\Approved\Approved On: 05-Nov-2025 14:15 (GMT)

Abbreviations: CRS: cytokine release syndrome; ICANS: Immune effector Cell Associated Neurotoxicity Syndrome; SUD: step-up dosing.

Notes:

1. Variable will be measured as incident and prevalent. Incident cases have a 30-day washout period applied.

Table 8. Variables for Outcomes (Objective 6 - Infections)

Variable	Role	Data Source	Operational Definition	
			Definition	Assessment Period(s)
Infection occurrences ¹	Outcome	MDV	Disease code for infections; the list of infections of interest will be outlined in the SAP (Yes/No) Incidence and prevalence will be reported, see Section 9.7.2 for additional details.	Follow-up period
Days from index to infection	Outcome	MDV	Time in days from index date to first infection (continuous)	Follow-up period
Days between infections	Outcome	MDV	Days between infection claims (continuous) For patients with ≥ 2 disease code for infections listed in the SAP during the time period	Follow-up period

Variable	Role	Data Source	Operational Definition	
			Definition	Assessment Period(s)
Antibiotics	Outcome	MDV	Health claim code for antibiotic treatment (Yes/No)	Follow-up period
Antivirals	Outcome	MDV	Health claim code for antiviral treatment (Yes/No)	Follow-up period
Antifungals	Outcome	MDV	Health claim code for antifungal treatment (Yes/No)	Follow-up period

Notes:

1. Variable will be measured as incident and prevalent. Incident cases have a 60-day washout period applied.

Table 9. Variables for Outcomes (Exploratory Objective 1 – Supportive Medications)

Variable	Role	Data Source	Operational Definition	
			Definition	Assessment Period(s)
Dexamethasone	Outcome	MDV	Health claim code for dexamethasone (Yes/No)	SUD period
Diphenhydramine	Outcome	MDV	Health claim code for diphenhydramine (Yes/No)	SUD period

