Acetaminophen	Outcome	MDV	Health claim code for acetaminophen (Yes/No)	SUD period
Tocilizumab	Outcome	MDV	Health claim code for tocilizumab (Yes/No)	SUD period

Variable	Role	Data Source	Operational Definition	
			Definition	Assessment Period(s)
IVIG	Outcome	MDV	Health claim code for IVIG (Yes/No)	IVIG follow-up assessment period

Abbreviations: IVIG: intravenous immunoglobulin; SUD: step-up dosing.

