9.7.3. Relative Administration Intensity

RAI will be calculated as the cumulative frequency of administration received over the expected number of administrations. Since response is needed to determine if switching to bi-weekly doses is appropriate and is not available in MDV, two schedule definitions will be used to estimate the expected number of administration to calculate RAI (Table 10. Dosing Schedule of Elranatamab during Follow-up Period for Patients Switching to

Q2W and Table 11. Dosing Schedule of Elranatamab during Follow-up Period for Patients staying on

QW Table 10. Dosing Schedule of Elranatamab during Follow-up Period for Patients Switching to

Q2W).

$$\text{RAI} = \frac{\text{Number of administrations received}}{\text{Number of expected administrations during the time period}}$$

a) Schedule 1¹

Assumption that all patients switch to bi-weekly doses (Q2W) after day 169 post-index.

Table 10. Dosing Schedule of Elranatamab during Follow-up Period for Patients Switching to Q2W

Follow-up Sub-Periods	Expected Administrations	Vial Size
Index date - Day 8	3 administrations	2 x 44mg/1.1mL 1 x 76mg/1.9mL
Day 9 - Day 168	1 administration per week	76mg/1.9mL
Day 169 – End of follow-up	1 administration every two weeks	76mg/1.9mL

Notes:

090177e1a4a71ff1\Approved\Approved On: 05-Nov-2025 14:15 (GMT)

¹ Adapted from dosing and administration guidance of the Japanese elranatamab label available at <https://labeling.pfizer.com/ShowLabeling.aspx?id=20462>

b) Schedule 2¹

Assumption that all patients continue with weekly doses (QW) after day 169 post-index.

Table 11. Dosing Schedule of Elranatamab during Follow-up Period for Patients staying on QW

Follow-up Sub-Periods	Expected Administrations	Vial Size
Index date - Day 8	3 administrations	2 x 44mg/1.1mL 1 x 76mg/1.9mL
Day 9 – End of follow-up	1 administration per week	76mg/1.9mL

Notes:

¹ Adapted from dosing and administration guidance of the Japanese elranatamab label available at <https://labeling.pfizer.com/ShowLabeling.aspx?id=20462>

Treatment exposure will be assessed across the different follow-up periods. End of follow-up is defined as the end of the hospital claim of the last elranatamab administration inclusive.

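### Table 7 identifies CRS and ICANS medications by a disease code, and the Table 9 drug window does not match the 14-day CRS/ICANS window

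*Protocol*

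**What the plan says.** **Medication given with an event.** In Table 7 (Objective 5, under Covariates and Outcomes) the CRS concomitant-medication outcome is "Disease code for concomitant medications (i.e., IV hydration) received on the same day as the CRS event (Yes/No"). The ICANS row has the same wording. Both rows are assessed in the CRS/ICANS follow-up assessment period.

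**Event window.** Section 9.2 gives "CRS/ICANS follow-up assessment period: defined as the 14-day window post index date", shortened if less data are available. Tables 2 and 7 apply it to all CRS and ICANS outcomes, reported for Group A, Group A+B and Group C.

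**Drug window.** Table 9 (Exploratory Objective 1) lists "Health claim code for tocilizumab (Yes/No") and "Health claim code for dexamethasone (Yes/No"). Both are assessed in the SUD period, which Section 9.2 runs between the "first 44mg/1.1mL vial of elranatamab and first 76mg/1.9mL vial of elranatamab, inclusive". Table 2 reports them for the same three groupings as CRS and ICANS.

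**Expected timing.** Table 10 in Section 9.7.3 places all three initial administrations, including one 76mg vial, in the sub-period "Index date - Day 8".

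**Objective wording.** Objective 5 in Section 8 still places CRS and ICANS in the SUD period, not in the 14-day window.

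**The concern.** There are two separate faults.

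1. The Table 7 medication variables name a code type that cannot return a medication. Section 9.3 leaves the code lists to the SAP, but the protocol itself fixes the type of code, and Section 9.8 says the protocol will be strictly followed.

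2. Section 7 gives adverse event management as one of the things the study will describe. Readers will therefore naturally set CRS frequency by SUD group beside tocilizumab and dexamethasone use by SUD group. The first is measured over a fixed window. The second is measured over a window whose length depends on the dosing intervals, and those intervals largely define the groups. A difference between groups in drug use relative to CRS could then come from the number of days observed and not from practice.

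**Working it through.** The protocol states no figure for this point, so there is nothing to reproduce. The check sets the definitions side by side and then counts days.

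**Code type.**

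| Variable | Place | Identified by |
|---|---|---|
| Earlier MM drugs, IVIG, anti-infectives | Table 3 | health claim code |
| MM drugs and IVIG in follow-up | Table 6 | health claim code |
| Antibiotics, antivirals, antifungals | Table 8 | health claim code |
| Dexamethasone, diphenhydramine, acetaminophen, tocilizumab, IVIG | Table 9 | health claim code |
| CRS and ICANS concomitant medications | Table 7 | disease code |

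Elsewhere in Tables 3, 7 and 8 a disease code marks a condition: hypertension, CRS, ICANS, cytopenias, infections. The two Table 7 medication rows are out of line with the rest of the protocol.

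**Windows: inputs.**
- Index is day 1 and is taken to be the first 44mg vial (assumption).
- *a* is the number of days from the first to the second 44mg vial. *b* is the number of days from the second 44mg vial to the first 76mg vial.
- Group A (Table 1): *a* and *b* each 1 to 7.
- Group B (Table 1): one or both of *a*, *b* from 8 to 14. The other, if not in that range, is taken as 1 to 7.
- Group C, extremely untimely (Table 1): *a* or *b* above 14.
- Last day of the event window: *L* = 14. *L* = 15 is also tried, in case the window means index plus 14 days.

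**Formula.** Last day of the SUD period = 1 + *a* + *b*. If this is below *L*, the event window has days without Table 9 drug capture. If it is above *L*, drugs are counted on days when CRS and ICANS are not.

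**Expected schedule, first 76mg vial on day 8.** Days without drug capture: 14 − 8 = 6, and 6/14 = 43% of the window. With *L* = 15: 15 − 8 = 7, and 7/15 = 47%.

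**All whole-day interval pairs.**

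| Group | Pairs | Day of first 76mg vial | Before day 14 | On day 14 | After day 14 |
|---|---|---|---|---|---|
| A | 7 × 7 = 49 | 3 to 15 | 46 | 2 | 1 |
| B | 14 × 14 − 49 = 147 | 10 to 29 | 20 | 10 | 117 |

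- Group A: up to 14 − 3 = 11 event days lack drug capture, and the excess is at most 15 − 14 = 1 day.
- Group B: at most 14 − 10 = 4 event days lack drug capture, and the drug window can run 29 − 14 = 15 days past the event window.
- Group C, extremely untimely: the earliest first 76mg vial is day 1 + 15 + 1 = 17, always past the window. Table 12 in Annex 2 puts the limit at 14 days or more, which gives day 1 + 14 + 1 = 16, also past it.
- The other two Group C types have no interval requirement and can fall either way.

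With *L* = 15 the pattern holds. Group A has 48 of 49 pairs before, 1 equal and 0 after. Group B has 30 before, 12 equal and 105 after.

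These pairs are possible schedules, not patient frequencies.

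**The case against.** The strongest reply has five parts.

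- **Table 9 does what its objective says.** Exploratory Objective 1 concerns supportive medication in the SUD period. No Table 9 drug is tied to a CRS event, and no proportion of treated CRS is planned from it. This stands. A reader might infer that the plan will report too low a share of CRS cases treated; the protocol plans no such statistic, so that inference is not supported. What remains is that the two sets of results share groupings but not days.
- **The Table 7 medication variables already use the 14-day window.** This also stands, so the window mismatch does not touch them. Their fault is the code type. The only example they name is IV hydration, so the protocol does not show whether tocilizumab or dexamethasone is included.
- **The SAP may settle it.** Code lists are left to the SAP, and Section 9.7 lets the SAP modify the plans. That answers a missing list. It does not make the protocol's stated code type correct.
- **The same-day rule is deliberate.** One might read it as too narrow, since treatment begun the next day scores No. But the amendment table describes medication at the same time as the event, and a same-day rule fits that. It can also pick up drugs given that day for other reasons, so its error is not purely in one direction. The documents give no basis for a particular longer window.
- **Tocilizumab is not the only hint of severity.** Correct: Table 7 also records length of stay for CRS events and their frequency.

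**Conclusion.** The point holds as two definition faults.

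1. The CRS and ICANS concomitant-medication outcomes name the wrong code type. Applied literally they would be empty. This is an error of definition, not a bias with a size.

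2. The Table 9 window for tocilizumab and dexamethasone is not aligned with the CRS/ICANS window. With the first 76mg vial on day 8, drug capture stops 6 of 14 days early. In most Group B interval pairs and all extremely untimely Group C schedules it continues past the event window. Group A+B pools both directions in one column.

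It is tempting to conclude that treatment of CRS is understated throughout. The documents do not support that: the direction depends on SUD length and reverses between groups. Nor is 43% a share of events or treatments. It counts calendar days under the expected schedule. The protocol gives no distribution of CRS onset, treatment dates or dosing intervals, so the effect on numbers of treated patients cannot be computed.

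The day counts rest on index being the first 44mg vial and on an event window ending on day 14; ending it on day 15 leaves the pattern unchanged.

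**What to change.** - **Table 7.** For both the CRS and the ICANS concomitant-medication variables, replace the disease code with a health claim code, and state whether tocilizumab and dexamethasone are included.
- **Tables 2 and 9.** Add the CRS/ICANS follow-up assessment period for tocilizumab and dexamethasone, beside the SUD period already planned. Show the two drugs separately, because dexamethasone may include premedication.
- **Objective 5.** Reconcile its SUD-period wording with the 14-day window used for CRS and ICANS in Tables 2 and 7, wherever the objective is stated.

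The cost is table wording and one more window to program and report. Data source, study population and the existing SUD-period results are unchanged.

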- **Study design:** This is a retrospective observational study utilizing de-identified data from Japan Hospital administrative claims data (Medical Data Vision [MDV]).
- **Population:** The study population will include all adults aged 18 years or older with an MM diagnosis who initiate elranatamab on or after March 26, 2024 (PMDA Elrexfio approval date). Patients with evidence of clinical trial participation will be excluded.
- **Variables:** The following variables will be summarized and reported:

Exposure of interest:

Exposure is defined as at least one record of a hospital claim for elranatamab on or after March 26, 2024. All patients included in the study will be considered exposed. Analyses of outcomes during the SUD period will also be stratified based on types of elranatamab exposure during that time (i.e., complete and timely SUD, complete but not timely SUD, alternative SUD). Clinical data will be collected from MDV hospital data.

Study outcomes:

Study endpoints include: elranatamab timing and dosing (i.e., types of doses, time between doses, relative administration intensity), HCRU and costs (i.e., IP/OP/ED claims and associated costs, degree of nursing), other MM treatment post elranatamab administration (i.e., PIs, SCT, supportive therapy), known adverse events (i.e., CRS events occurrence, frequency and associated length of stay, time from index to CRS event), infection (i.e., infection occurrence, time from index to infection, antibiotics), and supportive medication (i.e., IVIG, acetaminophen, dexamethasone).

Covariates:

Covariates will include baseline demographics (i.e., age, sex, weight etc.), and baseline clinical characteristics (i.e., comorbidities and treatment history).

- **Data sources:** The MDV database is a comprehensive resource containing administrative data from over 540 hospitals in Japan. This dataset includes information on demographics, mortality, labs, IP, OP, ED claims, treatments, procedures and costs of approximately 50 million patients. MDV is an aggregated, de-identified dataset where no patient can be individually identified and therefore no patient consent is required.
- **Study size:** This is a retrospective descriptive study with no a priori hypotheses; therefore, sample size calculations are not applicable. As of February 2025, MDV included 128 patients that had at least one hospital claim for an elranatamab administration.

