1.1.2. Covariates and Outcomes

Table 3 to Table 9 includes definitions and assessment periods for all study variables and that will be used to address the study objectives. Variables for which summary statistics across individuals are produced are identified in the table below. If applicable, the frequency and percentage of patients with missing data for each variable will be described.

Table 3. Variables for Baseline Characteristics (Objective 1 – Patient Characteristics)

090177e1a4a71ff1\Approved\Approved On: 05-Nov-2025 14:15 (GMT)

Variable	Role	Data Source	Operational Definition	
			Definition	Assessment Period
Age	Baseline characteristics	MDV	
Age at index date, in years.
 
Age will be reported as a continuous variable as well as a categorical variable for the following age groups:
 
 • <65 • 65-69 • 70-74 • ≥75 	Index date
Sex	Baseline characteristics	MDV	
Sex, N (%)
 
 • Male • Female 	Index date
Weight	Baseline characteristics Sub-group identifier	MDV	Weight assessment before and closest to the index date, lb	Baseline period
Height	Baseline characteristics	MDV	Height assessment before and closest to the index date, cm	Baseline period
Smoking index	Baseline characteristics	MDV	
Smoking index assessment before and closest to the index date
 
Smoking index = Number of cigarettes smoked * years of smoking
	Baseline period
Care setting	Baseline characteristics	MDV	
Care setting for the first elranatamab administration
 
 • Inpatient (IP) • Outpatient (OP) 	Index date

090177e1a4a71ff1\Approved\Approved On: 05-Nov-2025 14:15 (GMT)

Variable	Role	Data Source	Operational Definition	
			Definition	Assessment Period
Hospital scale	Baseline characteristics	MDV	Number of hospital beds in hospital admitted at index date (categorical) 
 • ≤199 beds • 200-499 beds • ≥500 beds 	Index date
Hospital category	Baseline characteristics	MDV	Hospital category at index date (categorical) 
 • University hospital • Public hospital (local) • Public hospital (National) • Private hospital 	Index date

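### CRS length of stay lacks the inpatient condition that the ICANS and all-cause stay variables carry, and neither event row isolates event-related days

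*Protocol*

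**What the plan says.** All of this is in the Protocol.

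- **CRS stay (Table 7):** "The total time in days of the CRS hospital stays among patients who have at least 1 CRS event (continuous". There is no inpatient condition.
- **ICANS stay (Table 7):** the same kind of total, but taken "among patients who have at least an IP stay with ≥ 1 ICANS event".
- **All-cause stay (Table 5 and section 9.7.4):** limited to patients with at least one inpatient stay or visit.
- **Event identification (Table 7):** "Disease code for CRS (Yes/No"), with no restriction on setting.
- **Window (section 9.2):** "CRS/ICANS follow-up assessment period: defined as the 14-day window post index date", shortened where less data are available. Table 7 gives this as the assessment period for both stay variables.
- **Purpose (Abstract):** "CRS events occurrence, frequency and associated length of stay, time from index to CRS event".
- **Setting (Table 3):** "Care setting for the first elranatamab administration" is recorded as inpatient or outpatient.
- **Onset (Table 7):** days from index to the first CRS event and to the first ICANS event are separate variables. Neither is used in the stay definitions.
- **Reporting (Table 2):** Objective 5 is reported for Group A, Group A+B and Group C.

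**The concern.** Two parallel rows of one table answer different questions. The ICANS row gives the length of stay of patients who were in hospital with the event. The CRS row, taken literally, gives hospital days per CRS patient, admitted or not. The protocol offers no reason for the difference, and the CRS row is the only length-of-stay variable without an inpatient condition. A reader who sees the two results in one table will assume that they are on the same basis.

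The numerator has a separate weakness, which CRS and ICANS share. Nothing starts the count at onset. If a patient is admitted for step-up dosing and the event follows some days later, the days already spent in hospital belong to the stay. The result then mixes planned admission with event-related stay. Because results are shown by step-up dosing group, a difference in planned admission between groups could look like a difference in event burden.

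Finally, the table does not say what the 14-day window does to a stay that outlasts it. Two programmers could produce different numbers from the same row.

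**Working it through.** The protocol states no length-of-stay figure, so there is none to reproduce. The check compares the definitions and then shows, on assumed values, what each open reading does to the result.

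**Step 1: populations side by side**

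| Variable | Place | Population |
|---|---|---|
| CRS stay | Table 7 | at least one CRS event, any setting |
| ICANS stay | Table 7 | an inpatient stay with an ICANS event |
| All-cause stay | Table 5 | at least one inpatient stay |
| All-cause stay | Section 9.7.4 | at least one inpatient visit |

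CRS is found by a disease code in any setting, and first administration may be outpatient. CRS without admission is therefore possible under the protocol's own definitions.

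**Step 2: effect of the denominator**

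Let L be the mean stay among CRS patients with an inpatient CRS stay, and f their share of all CRS patients. Neither is given in the documents. If patients without admission count as 0 days:

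mean under the CRS wording = f × L; mean under the ICANS wording = L.

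With L = 10 days (assumed):

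| f | CRS wording | ICANS wording |
|---|---|---|
| 1.0 | 10.0 | 10.0 |
| 0.9 | 9.0 | 10.0 |
| 0.7 | 7.0 | 10.0 |
| 0.5 | 5.0 | 10.0 |

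As a worked case, take six patients with 10 days and four never admitted. The CRS wording gives (6 × 10 + 4 × 0) / 10 = 6.0 days; the ICANS wording gives 60 / 6 = 10.0 days. The difference vanishes if f = 1 or if patients without admission are left out.

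**Step 3: days before onset**

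Days from onset = length of stay − days in hospital before onset. For an assumed 10-day stay with 0, 2 or 4 days in hospital before onset, this gives 10, 8 or 6 days. The whole-stay count exceeds it by 0, 2 or 4 days. The same holds for ICANS.

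**Step 4: the window**

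Take an assumed stay from day 10 to day 24. If the window only selects events, the stay counts 24 − 10 + 1 = 15 days. If it also cuts days at day 14, the stay counts 14 − 10 + 1 = 5 days. These are alternatives: a stay cannot be counted in full and also be cut. The text does not choose between them.

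**The case against.** The strongest reply has four parts.

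- **Zeros are not stated.** A patient with no CRS hospital stay could just as well contribute no value, which would match the inpatient convention of section 9.7.4. This is fair: the 0-day result is the literal reading, not an explicit rule. But section 9.7.4 concerns all-cause stay, and the ICANS row spells out the inpatient condition that the CRS row omits. The wording still needs aligning.
- **Whole-stay length is legitimate.** The Abstract promises stay associated with CRS, not attributable to it, and total length of admissions carrying a code is a recognisable claims measure of association. This stands. A reader might infer that the variable does not measure CRS-associated stay at all; the documents do not support that. The supportable statement is that neither row isolates event-related days.
- **The rest belongs to the SAP.** How stays are linked to codes, and how days outside the window are handled, may be settled there. That covers the operational detail. It does not cover the two populations, which Table 7 itself fixes differently.
- **The consequence is small.** The study makes no formal comparisons and plans no CRS-versus-ICANS contrast. Medians, quartiles and ranges accompany the mean, and care setting and time to event are reported separately. This limits the harm. But in the worked case of six 10-day stays and four zeros, the median stays at 10 only because fewer than half the values are zero, and the lower quartile falls to 0.

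**Conclusion.** The point holds as a mismatch of populations in Table 7 plus two counting rules left open. The mismatch is on the face of the document. The inclusion of days before onset is the plain reading of both rows, though not an express statement, and it applies to CRS and ICANS alike.

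Two further inferences are tempting and unsupported. One is that prolonged stays are truncated at day 14; that is only one reading of the window. The other is that the CRS mean mostly reflects where step-up dosing was given. Table 3 records the setting of the first administration only, an outpatient initiator admitted for CRS has a real stay, and the documents give no inpatient share, CRS frequency or stay length.

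The size therefore cannot be derived. The illustrations (a mean between 10.0 and 5.0 days as f goes from 1.0 to 0.5, and an excess of 0 to 4 days before onset) rest wholly on assumed values. The endpoint is secondary and descriptive, so the effect is on how the figure is read. It is worth correcting because the reported number can change and the correction is cheap.

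**What to change.** 1. Use one denominator for both rows of Table 7: patients with at least one inpatient stay with the event.
2. Report separately the number of patients with the event but no inpatient stay.
3. State that the 14-day window selects events and that the selected stay is followed to discharge.
4. Label the existing measure as total length of admissions with a CRS or ICANS code, and report beside it the inpatient days from the first event code to discharge.

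A reference line showing total stay in inpatient initiators without the event, by step-up dosing group, would help but is optional. It is an added analysis in a small sample: 128 patients had an elranatamab claim at the February 2025 data cut.

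The cost is an edit to Table 7 and a little programming. The event dates are already needed for the time-to-event rows, and stay durations for the stay rows. There are two downsides. Code dates may mark onset imprecisely, since section 9.9 warns of coding errors and of timing inaccuracies that matter most over short periods. Days from first code to discharge may also still include planned inpatient days. Reporting both measures together makes these limits visible.
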